## A Introduction

### A1 Study Abstract and Background

The prevalence of youth-onset type 2 diabetes (T2D) is on the rise, especially in minority and disadvantaged populations. During the COVID-19 pandemic there was a further increase in youth-onset T2D, likely due to more sedentary behaviors. Family history of diabetes, quality of and access to health care, differences by race/ethnicity in insulin sensitivity, diet quality, and minimal physical activity are some of the risk factors for T2D. Furthermore, T2D in youth has been found to be more aggressive in nature with rapid deterioration in  $\beta$ -cell functioning and high rates of diabetes complications, compared to T2D in adults. Given the clinical course of youth-onset T2D and limited treatment options (metformin, insulin or subcutaneous GLP-1 agonist), there is an increasing need for interventions that not only improve glycemic control and reduce insulin resistance, but also promote behavioral modifications such as exercise and healthy eating.

In youth with type 1 diabetes (T1D), the use of continuous glucose monitoring (CGM) has been associated with decreased hemoglobin A1c (HbA1c) levels and increased time in range (TIR), while also improving quality of life. Similar trends have been noted in adults with T2D, in which investigators concluded that the real-time glycemic feedback provided by CGM gave way to lifestyle modifications, including more physical activity, that led to improvements in glycemic control. The SEARCH study found that most youth with T2D test their glucose levels fewer than 3 times per day and 27% of youth with T2D had poor glycemic control (HbA1c > 9.5%).

Given the improvements observed when implementing CGM in youth with T1D and adults with T2D, there is reason to believe that CGM could play a pivotal role in helping youth with T2D check their blood sugars more frequently, while also promoting behavioral modifications that improve glycemic control. There is limited information on the use of CGM in youth with T2D.

We conducted a pilot clinical trial to determine if a complementary 10-day trial of CGM use in youth with T2D impacts glycemic control and behavior.

### A2 Primary Hypothesis

We hypothesize that providing sample complementary CGM at the point of care with standardized CGM education will improve glycemic control in pediatric patients with type 2 diabetes.

## B Study Objectives

### B1 Primary Aim

To determine if 10-day trial CGM use in youth with T2D improves glycemic control (changes in time in range and Hemoglobin A1c).

---

## ***B2 Secondary Aim***

To determine if 10-day trial CGM use in youth with T2D improves measures of diabetes distress and diabetes related quality of life.

---

## **C Study Design**

### ***C1 Overview of Study Design***

This is a hypothesis-driven, pre-registered, prospective cohort study to determine if point of care placement of complementary CGM with standardized CGM education improves glycemic control.

The study will consist of a baseline visit (coincident with routine clinical care) where a complementary trial CGM is placed at the point of care with standardized CGM education. CGM-related apps will be downloaded on the participant's smartphone. Follow-up phone calls will be conducted by the study team at 5-days and 10-days after CGM placement. CGM data will be recorded at the next follow-up visit (if available) and hemoglobin A1c level (performed as part of routine clinical care) recorded. Surveys will be completed at baseline, 10-days (via email), and at follow-up (3-6months)

### ***C2 Subject Selection and Withdrawal***

#### **2.a Inclusion Criteria**

- Patients with type 2 diabetes for more than 3 months
- Ages 8-21 years
- CGM naive or no CGM use in the 12 months prior to enrollment
- No minimum A1C level required for eligibility.

#### **2.b Exclusion Criteria**

- CGM use in the 12 months prior to enrollment
- Participants with T2D not on insulin

#### **2.c Subject Recruitment Plans and Consent Process**

Individual(s) responsible for approaching participant(s): Research coordinators

Where and when recruitment will take place:

Participants will be recruited, screened for eligibility, and consented in a private clinic/room to ensure privacy.

Consent process:

Participants will read through the consent form with the research coordinator, have time to review it and ask questions about the study and study procedures.

#### **2.d Randomization Method and Blinding**

Not applicable

---

**2.e Risks and Benefits**

This study involves no more than minimal medical risk to the participants as use of CGM is considered standard of care per the American Diabetes Association guidelines.

Risks associated with use of CGM may include hypoglycemia (low blood sugar) or hyperglycemia (high blood sugar) in cases where information provided by the CGM device is inaccurate and used to make treatment decisions or where hardware or set-up issues disable alarms and alerts. Patients will be advised to confirm with a fingerstick blood sugar if symptoms do not match CGM readings.

Patients may also experience skin irritation or redness around the CGM device's adhesive patch. The CGM may inadvertently fall off, and if that occurs, the patient will resume checking fingerstick blood sugars as they were previously.

To minimize risk, when the diabetes nurse/CDCES places the CGM, the nurse will perform routine standardized education including setting up alerts. The CGM devices provide blood sugars every 5 minutes (that creates a continuous reading) versus the typical 4-5 fingerstick blood sugars usually checked per day. Therefore, the CGM actually minimizes risk of hypoglycemia by alerting users to impending hypoglycemia which may not have been previously detected. Participants will have been taught signs/symptoms of hypoglycemia per routine new-onset diabetes education. They will be educated to check blood sugar via fingerstick if they have any sign/symptoms of hypoglycemia and treat accordingly. If they do not understand how to use the device, they have access to Pediatric Endocrinology on-call provider and Dexcom customer service for assistance, and device may be removed early. The risk of device malfunction is extremely low.

The CGM will be applied in clinic by diabetes nursing staff. If patient reports any irritation or signs of infection at the site, the CGM will be removed early. If the CGM is removed early either accidentally or intentionally, participants will be offered a replacement CGM. They will have to resume previous blood sugar monitoring with glucometer and fingersticks, as the patient was using prior to placement of CGM.

**Confidentiality:** There is the risk that psychological, emotional, financial, social, and legal risks might result if confidentiality cannot be maintained in this study. All study team members are HIPPA trained and will take every step to respect participants' privacy and protect their confidentiality throughout the study. We share the information gathered in the study only with the people who need to know this information. All information gathered during this study will be kept in a secure HIPAA compliant database, REDCap.

**Benefit:** Use of CGM may increase blood sugar monitoring, reduce hypoglycemia, and improve glycemic control.

**2.f Early Withdrawal of Subjects**

Participants may withdraw from the study at any time by notifying the study team.

**2.g When and How to Withdraw Subjects**

The participant may choose to withdraw from the study. It will also not impact the course of the participant's clinical care.

## **2.h Data Collection and Follow-up for Withdrawn Subjects**

Data collected from subjects will remain in the dataset, but no follow-up will be conducted on withdrawn subjects.

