### **D2 Schedule of Procedures**

**Eligibility and Consent:** If the patient is eligible and interested in the study, the research coordinator will meet with the patient and caregiver in an exam room for privacy and confidentiality. The research coordinator will explain the study and study procedures, read the informed consent form with the participant and caregiver, and allow time for questions on the study and consent form.

If the participant is less than 18 years of age, the parent will sign the consent form and the participant will sign the assent. If the participant is 18 years of age or over, the participant will sign the consent.

At the time of consent, 3 phone numbers are collected from the participant for future follow-up.

At the baseline visit, barriers to prior CGM use or sustained use will be recorded.

The certified diabetes educator (CDCES) will place the CGM and provide standardized education, including education on use of the Dexcom apps, including Dexcom G6 Dexcom Clarity, and Dexcom Follow (optional) for caregivers. The participant's Dexcom Clarity account will be connected to the clinic portal for remote viewing of data.

The nurse/CDCES will follow up with the patient by phone in 5 days (4-6 days if day 5 falls over a weekend) and again at 10 (9-11) days at the end of the CGM session. Assessment and education during these follow-up phone calls will include report of behavior changes related to blood glucose monitoring and insulin administration, and nurse/CDCES recommended dose adjustments based on observed patterns, as well as education on obtaining personal CGM. CGM data (when available) will be recorded.

---

At the participant's next follow-up visit at 3 months (or up until 6 months if a visit is cancelled), use of personal CGM will be recorded, in addition to Hemoglobin A1c measured at that visit, questions about behavioral changes, and CGM data, if available.

Questionnaires will be administered before and after initiation of the CGM and at their routine diabetes clinic visit 3-months later to assess changes in psychosocial outcomes of diabetes distress and hypoglycemia worry. Surveys will be administered via REDcap survey.

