### **E. Statistical Plan**

#### ***E1. Sample Size Determination and Power***

We calculated the sample size to detect a 10% difference in TIR from the first 5-days compared to the second 5 days of CGM wear. Assuming a TIR SD of 18% (20), a 2-sided alpha level of 0.05 and 80% power, a sample size of 28 participants was required. Allowing for 30% attrition, we planned to recruit 40 participants.

---

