## ***E3. Analysis Plan***

Primary outcome variable.

The primary outcomes of the study were change in TIR from the first 5 days compared to the second 5 days of CGM wear, and change in HbA1c level from baseline to follow up at 3-6 months, both assessed with paired *t*-tests.

Secondary outcome variables.

Secondary endpoints included behavioral modification assessed via questions during 5-day and 10-day follow up call. Change in patient-reported outcomes through surveys assessing quality of life and diabetes-distress compared between baseline and follow-up after trial CGM use.

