## ***E5. Missing Outcome Data***

Dataset will be assessed for missing-ness and noted in results. Statistical tests will be performed to compare groups with and without missing data, to assess for data missing at random.

---

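### Section 2.h ends follow-up at withdrawal without asking whether routine-care HbA1c may still be used, so a primary outcome value that may already be in the chart can be lost

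*Combined protocol and SAP*

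**What the plan says.** Under section 2.f a participant withdraws by telling the study team. Section 2.g adds, on withdrawal: "It will also not impact the course of the participant's clinical care". Section 2.h then sets the data rule: "Data collected from subjects will remain in the dataset, but no follow-up will be conducted on withdrawn subjects". None of these sections lets a participant leave study procedures while still permitting record review.

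One of the two primary outcomes in section E3 is "change in HbA1c level from baseline to follow up at 3-6 months", tested with a paired t-test. Section C1 describes the follow-up measurement as "hemoglobin A1c level (performed as part of routine clinical care) recorded". Section D2 places it "At the participant's next follow-up visit at 3 months (or up until 6 months if a visit is cancelled".

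On missing outcomes, section E5 says that missingness will be noted and that "Statistical tests will be performed to compare groups with and without missing data, to assess for data missing at random". It plans no imputation and no sensitivity analysis, and sections E3 and E4 name no analysis population for HbA1c.

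Section E1 allows for 30% attrition. It does so in a calculation for time in range (TIR), and it does not divide the 30% by cause.

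**The concern.** Withdrawal rules usually stop follow-up because further data would need further visits from someone who has declined them. That reason does not apply to this HbA1c. The clinic measures it whether or not the person is in the study, and the study only copies it from the record. A participant who withdraws and later attends clinic in the 3-6 month window has the outcome on file, yet 2.h as ordinarily read stops the study from using it.

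The loss matters because a paired t-test needs both values. A withdrawn participant's baseline HbA1c stays in the dataset but contributes nothing to the primary result, which becomes an estimate for people who stayed. The study has one arm, so no control group shares the attrition and partly offsets it. Any difference between leavers and stayers goes straight into the estimate.

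**Working it through.** **1. The plan's own figure.** Inputs from section E1: TIR difference 10, SD 18, two-sided alpha 0.05, power 80%.

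- Normal approximation: n = (18 × (1.960 + 0.842) / 10)² = 25.4, rounded up to 26.
- Exact paired t (noncentral t, standardized effect 10/18 = 0.556): power is 0.794 at n = 27 and 0.809 at n = 28, so n = 28. This matches the plan.
- Attrition: 28 / (1 − 0.30) = 40. This also matches.

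The plan therefore allows for up to 40 − 28 = 12 participants who are not evaluable for TIR. Nothing in this point changes the sample size.

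**2. Whom the rule reaches.** Section 2.f makes withdrawal an active notice to the team. Section 2.e deals separately with early sensor removal, accidental or intentional: a replacement is offered and the person returns to fingersticks. No section treats a missed call or unanswered survey as withdrawal. These participants stay enrolled, and their HbA1c is recorded under C1 and D2. Only people who say they are leaving fall under 2.h.

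**3. Effect on the mean.** Let w of 40 enrolled participants withdraw, with all others having both values. Let G be the mean HbA1c change in completers minus that in withdrawn participants. Then

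shift = (completer mean) − (mean of all enrolled) = (w / 40) × G.

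The documents give neither w nor G, so both are assumed. A negative shift flatters the intervention.

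| Withdrawn (w) | w / 40 | G = −0.5 | G = −1.0 | G = 0 | G = +0.5 |
|---|---|---|---|---|---|
| 2 | 0.05 | −0.025 | −0.05 | 0 | +0.025 |
| 4 | 0.10 | −0.05 | −0.10 | 0 | +0.05 |
| 6 | 0.15 | −0.075 | −0.15 | 0 | +0.075 |
| 12 (all of the 30%) | 0.30 | −0.15 | −0.30 | 0 | +0.15 |

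**4. Effect on precision.** The standardized paired change detectable with 80% power (two-sided 0.05, exact t) is 0.549 SD at n = 28, 0.511 at n = 32, 0.480 at n = 36 and 0.454 at n = 40. Going from 28 to 40 would require all 12 lost participants to be withdrawals who attend clinic in the window and permit use of the record.

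**5. Whether the E5 check would protect the result.** It compares observed characteristics and does not recover outcomes. It is also weak at this size. A two-sample t-test of 12 missing against 28 present has 80% power only for a difference of about 0.99 SD; with 4 against 36, about 1.5 SD. A non-significant result would not show that the data are missing at random.

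**The case against.** The strongest reply is that someone who actively leaves a study has asked for data collection to end, and that stopping there is a defensible default. A tiered withdrawal option is good practice, and its absence is not in itself an error. That stands, and it is why the fix depends on permission.

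Four further objections limit the point:

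- **Wording.** Ending follow-up could mean no further contact rather than no chart extraction. Section 2.h does not say. If the narrower meaning is intended, nothing is lost, but two coordinators could handle the same participant differently, which is itself a reason to rewrite the rule.
- **Availability.** The value exists only if the withdrawn person attends clinic within the window. People who miss that visit without withdrawing also lack a paired value, and no change to 2.h recovers them.
- **Consent.** The consent pages are not among the material reviewed, so they may already cover record use after withdrawal.
- **Timing.** Parts of A1, E1 and E3 are in the past tense. If enrolment is over, new wording cannot cover those who have already left.

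A reader might also infer that 2.h discards the HbA1c of anyone who stops wearing the sensor or stops answering calls. Sections 2.e and 2.f do not support that: such a person has not withdrawn. Or a reader might infer that the result is biased toward benefit because leavers probably found the device unhelpful. That is plausible, but the documents give no reasons for withdrawal and no outcomes for those who withdraw, so the bias could be zero or run the other way.

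**Conclusion.** The point holds in a limited form. For people who formally withdraw before the 3-6 month visit, 2.h on its ordinary reading gives up a primary outcome value that may exist in routine records, and neither E3 nor E5 compensates.

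The likely size is modest. With 2 to 4 withdrawals of 40 and an assumed 0.5-point gap between completers and withdrawn participants, the mean shifts by 0.025 to 0.05 HbA1c points, in a direction the documents do not settle. At that gap, 0.15 points is a limit. Taking it as the expected bias would treat the whole 30% as withdrawals, but that figure is total attrition set for the TIR calculation. E4 limits the TIR comparison to people with at least 8 days of wear, and those who fall short can still contribute HbA1c. The fall in detectable change from 0.549 to 0.454 SD is likewise a best case.

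This is a cheap improvement that avoids needless loss of primary outcome data. It does not show that the HbA1c result would be materially wrong.

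**What to change.** Rewrite section 2.h so that a participant who withdraws is asked whether the routine-care HbA1c at 3-6 months may still be taken from the clinic record.

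- If permission is given, record the value and include it in the primary HbA1c analysis.
- If it is refused, stop record collection at that point.
- State explicitly whether ending follow-up covers chart extraction as well as contact.
- Align the consent wording if it does not already allow this.
- Report withdrawals separately from missed clinic visits, so that a reader can see how much of the missing HbA1c comes from each.

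The cost is IRB review of the wording and a few chart look-ups. The change does not recover HbA1c for people who miss the clinic visit. It also cannot be applied to people who have already withdrawn unless there is permission or another approved basis for using their records; for them, the separate reporting is what remains.

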## **D Study Procedures**

### **D1 Screening for Eligibility**

Patients being seen in the diabetes center will be pre-screened for eligibility by the research team based on the inclusion criteria. Eligibility will be confirmed with the patient's diabetes provider at the time of the clinic visit, and with the potential participant based on the inclusion criteria. The study coordinator will confirm that the participant that they have never used a CGM, or have not used CGM in the prior 12 months and are currently on insulin therapy.

### **D2 Schedule of Procedures**

**Eligibility and Consent:** If the patient is eligible and interested in the study, the research coordinator will meet with the patient and caregiver in an exam room for privacy and confidentiality. The research coordinator will explain the study and study procedures, read the informed consent form with the participant and caregiver, and allow time for questions on the study and consent form.

If the participant is less than 18 years of age, the parent will sign the consent form and the participant will sign the assent. If the participant is 18 years of age or over, the participant will sign the consent.

At the time of consent, 3 phone numbers are collected from the participant for future follow-up.

At the baseline visit, barriers to prior CGM use or sustained use will be recorded.

The certified diabetes educator (CDCES) will place the CGM and provide standardized education, including education on use of the Dexcom apps, including Dexcom G6 Dexcom Clarity, and Dexcom Follow (optional) for caregivers. The participant's Dexcom Clarity account will be connected to the clinic portal for remote viewing of data.

The nurse/CDCES will follow up with the patient by phone in 5 days (4-6 days if day 5 falls over a weekend) and again at 10 (9-11) days at the end of the CGM session. Assessment and education during these follow-up phone calls will include report of behavior changes related to blood glucose monitoring and insulin administration, and nurse/CDCES recommended dose adjustments based on observed patterns, as well as education on obtaining personal CGM. CGM data (when available) will be recorded.

---

At the participant's next follow-up visit at 3 months (or up until 6 months if a visit is cancelled), use of personal CGM will be recorded, in addition to Hemoglobin A1c measured at that visit, questions about behavioral changes, and CGM data, if available.

Questionnaires will be administered before and after initiation of the CGM and at their routine diabetes clinic visit 3-months later to assess changes in psychosocial outcomes of diabetes distress and hypoglycemia worry. Surveys will be administered via REDcap survey.

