## ***E4. Statistical Methods***

Categorical variables will be described using frequencies and percentages. The Shapiro-Wilks test will be used to assess the normality distribution of continuous variables.

Normally distributed variables will be described by mean and standard deviation. Non-normally distributed variables will be described by median and interquartile range. Paired *t*-tests will be used to assess most differences between baseline and follow up. Wilcoxon signed rank tests will be used for the Diabetes Distress Scale scores and sub-scores.

Time in range data from the first 5 ( $\pm 1$ ) days of CGM wear will be compared to the second 5 ( $\pm 1$ ) days for any patients with at least 8+ days of CGM wear. Additional comparisons will be made with the follow-up CGM data recorded at the 3 or 6-month follow-up. Three month follow up data will be used when available. If the 3-month visit is missing, but there is a later 6-month follow-up, the 6-month visit data will be used. Two sample *t*-tests, and Wilcoxon rank sum tests (for the Diabetes Distress Scale), will be used to assess differences between groups in survey responses. The values  $p < 0.05$  are considered statistically significant. Statistical analysis generated using SAS version 9.4

Copyright © 2020 SAS Institute Inc., Cary, NC.

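### Does the quality-of-life half of the secondary aim go unmeasured because the procedures mention hypoglycemia worry instead?

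*Combined protocol and SAP*

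**What the plan says.** Three sections of the combined protocol and SAP describe what the surveys measure.

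- Section B2 (Secondary Aim) asks whether the 10-day CGM trial "improves measures of diabetes distress and diabetes related quality of life".
- Section E3 (Analysis Plan) lists, among the secondary endpoints, change in patient-reported outcomes through "surveys assessing quality of life and diabetes-distress compared between baseline and follow-up after trial CGM use".
- Section D2 (Schedule of Procedures) states "Questionnaires will be administered before and after initiation of the CGM", and again at the routine clinic visit three months later, "to assess changes in psychosocial outcomes of diabetes distress and hypoglycemia worry".

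Section C1 schedules surveys at baseline, at 10 days and at 3 to 6 months without saying what they contain. Section E4 (Statistical Methods) names one instrument: "Wilcoxon signed rank tests will be used for the Diabetes Distress Scale scores and sub-scores". For the rest, it says that paired *t*-tests "will be used to assess most differences between baseline and follow up". No quality-of-life scale and no hypoglycemia-worry scale is named. C1 opens with "This is a hypothesis-driven, pre-registered, prospective cohort study", while section A1 reports in the past tense: "We conducted a pilot clinical trial".

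**The concern.** Anyone checking aims against procedures would stop here. The aim and the endpoint give one pair of constructs and the procedures give another; only diabetes distress is common to both. Quality of life has no named scale, and hypoglycemia worry appears in no aim and no listed endpoint.

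Two consequences would matter if the worst reading were true. First, if the electronic survey had been built from D2 alone, there would be no quality-of-life score from before CGM placement. That score cannot be collected afterwards, so the comparison promised in E3 could not be made. Second, with no scale named, more than one score could later be presented as quality of life, or hypoglycemia worry could be promoted to an endpoint once the results were known. A study that calls itself pre-registered has reason to avoid both.

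**Working it through.** The question is mainly one of text, so the sections are set side by side.

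| Section | Diabetes distress | Quality of life | Hypoglycemia worry | Instrument or test |
|---|---|---|---|---|
| B2 Secondary Aim | yes | yes | no | none |
| C1 Overview | not specified | not specified | not specified | survey times only |
| D2 Procedures | yes | no | yes | none |
| E3 Analysis Plan | yes | yes | no | none for the surveys |
| E4 Statistical Methods | yes, scale named | not named | not named | signed rank for distress; paired *t*-test for most others |

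**Step 1: do the sections exclude one another?** For a true contradiction, D2 would have to say that quality of life is not measured, or that distress and hypoglycemia worry are the only constructs. It says neither. It is one sentence giving the purpose of the questionnaires. E3, by contrast, states directly that the surveys assess quality of life. The two can both be true: the union of the sections is three constructs (distress, quality of life, hypoglycemia worry), and none is ruled out anywhere.

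**Step 2: what would it take for quality of life to be lost?** The survey would have to be built from D2 while setting aside both the stated aim (B2) and the stated endpoint (E3). Nothing in the documents suggests this. C1 schedules the surveys at baseline without restricting their content, so a quality-of-life questionnaire included because of E3 would have its baseline value.

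**Step 3: does each construct have an analysis?** Distress has the signed rank test. Quality of life and hypoglycemia worry fall under E4's general provision for paired *t*-tests. That provision covers most differences and names neither score, so this is the natural reading and not an explicit assignment. No other paired test competes for them.

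**Step 4: does any design figure depend on the answer?** The only design figure is in section E1, and it concerns time in range: a difference of 10 percentage points, SD 18 (taken here as the SD of the paired difference), two-sided alpha 0.05, power 80%.

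- Normal approximation: n = (18 × (1.960 + 0.842) / 10)² ≈ 25.4, so 26.
- Exact paired *t*-test: power is 79.4% at n = 27 and 80.9% at n = 28, so 28 is the smallest sufficient number, as E1 states.
- Attrition: 28 / (1 − 0.30) = 40, as E1 states.

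No survey quantity enters these lines. Naming a quality-of-life scale would leave 28 and 40 as they are.

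**The case for a change.** The strongest case for acting runs as follows. Quality of life is half of the only secondary aim. D2 is the one procedures section that says what the questionnaires are for, so it is where survey builders would look. The baseline score cannot be recovered if missed. Naming a scale costs a line of text. Hypoglycemia worry cannot simply be assumed to stand for quality of life: the documents never say so, and a worry scale alone would be narrower than what B2 promises.

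Much of this stands. The descriptions are misaligned, the quality-of-life scale is unnamed in this text, and redefining hypoglycemia worry as the quality-of-life measure would narrow the aim to fit the procedures. A good report will name each instrument and score, present hypoglycemia worry as an additional exploratory outcome if it was collected, and say plainly if any construct in the aim lacked a baseline measurement.

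What does not stand is the step from there to a defect in the plan. Loss of the baseline is conjecture, because it requires the aim and the endpoint to be ignored. One could contrast about 28 evaluable pairs (40 × 0.70, assuming that E1's attrition also applies to surveys) with none, but the zero rests on the least likely reading. Whether outcomes could be chosen after the fact depends partly on the pre-registration, which cannot be seen here and may or may not name the scales. Parts of the text are in the past tense, which suggests the surveys may already have been given. If so, a change to D2 could not alter what was collected.

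**Conclusion.** No change to the plan follows. The sections describe the survey content unevenly, but none rules out quality of life, E3 affirms it, and E4 provides a usable paired test. No planned result, rule or figure is shown to be wrong. This is missing detail of a kind that the study team and its analysts fill sensibly by collecting what the aim and endpoint call for and naming the scales when they report.

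The reach is small: one of two constructs in a secondary aim of a single-group pilot. The time-in-range and HbA1c outcomes and the sample size are untouched. The conclusion assumes that the surveys were built with B2 and E3 in view and that E4's general provision is meant for survey scores other than the Diabetes Distress Scale. If quality of life proved not to have been measured at baseline, the report should state that it was not assessed and disclose any departure from the aim.
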